4.2. Inclusion and Exclusion Criteria

Inclusion Criteria

- Patient meets criteria for severe asthma:
 - On Global Initiative for Asthma (GINA 2021) Step 5 (8)
 - Uncontrolled on GINA Step 4, at least one of the following:

- poor symptom control: asthma control questionnaire ACQ>1.5, ACT<20 or "not well controlled" by National Education and Prevention Program [NAEPP]/GINA guidelines (8,9)
- airflow limitation: after appropriate bronchodilator withhold Forced expiratory volume in one second (FEV1) <80% predicted (in the face of reduced FEV1/forced vital capacity [FVC] defined as less than the lower limit of normal)
- serious exacerbations: at least one hospitalisation, intensive care unit (ICU) stay or mechanical ventilation in the previous year
- frequent exacerbations: two or more bursts of systemic corticosteroids (>3 days each) in the previous year

Exclusion Criteria

- For Objective (3), patients will be excluded if they have an unknown LTOCS status (objective 3 – although we will look at 'unknown' LTOCS that has been completed retrospectively to assess any potential for bias), if they have information on only 1 visit, and/or they are not taking LTOCS at their baseline visit (defined by first visit with LTOCS=yes). For Objective (4), patients will be excluded if they have unknown biologic status and/or none of the asthma severity indicators at baseline (defined by first visit with asthma severity indicator=yes)
- Patients (from some countries/regions) who have not consented for their data to be used for research purposes and/or data that have been approved for specific studies only.

5. Study Variables and Study Outcome Definitions

Objective 1: Proportion of patients on the ISAR with 100% completeness of key research variables from 2017 to latest date available

Outcome: Proportion of patients meeting 100% completeness of key research variables by patient status (i.e. new patients and follow-up visits)

Exposure: Time (calendar year and pre-specified periods of change)

Covariates: Country (numbers allowing), Country-specific factors (method of data provision, healthcare setting, date of participating in ISAR), visit-specific factors

We will focus on key research variables, as voted for in the 2023/24 Delphi exercise. For first visits or where patient starts or switches a biologic (**KPR visits**), 16 variables will be investigated (see **Table 1**). For **re-review (RR)** visits, 11 variables will be investigated.

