We will investigate the percentage of patients with 90% complete core variables in ISAR over time. The completeness of individual core variables will also be investigated, as well as

the proportion of individuals that meet criteria for $\geq 90\%$ completeness of core variables. There are 38 core variables in the ISAR, as voted for in the Delphi 2017 exercise. These are shown in **Appendix 1** (Section 13.1) along with some more information about the ISAR schedules. We will also investigate patient characteristics associated with completeness of data for targeted strategies.

Objective 3: Differential characteristics and proportion of patients on LTOCS in the ISAR registry over time

Outcome: Proportion of patients on LTOCS (at visit)

Exposure: Time (calendar year and pre-specified periods of change)

Covariates: Age, gender, country, country-specific factors

The characteristics of patients in the ISAR registry who are prescribed LTOCS are likely to change with policy initiatives, awareness of serious adverse events, increased knowledge about asthma among participating sites, and biologic availability. ISAR may also have prompted behaviour change among clinicians who treat patients with severe asthma thereby affecting their treatments and/or outcomes. We will assess trends in LTOCS use over time, adjusting for age and gender, and stratifying by country and country-specific factors (e.g. participation in ISAR consortium, data capture system). We will also evaluate proportion and time to stopping/reducing the dose ($\leq 5\text{mg}$) of LTOCS to assess differences in clinical practice over calendar time.

Objective 4: Severity of asthma in those initiating biologic treatment over time

Outcome: Initiation of biologic treatment by asthma severity indicator

Exposure: Time (calendar year and pre-specified periods of change)

Covariates: Age, gender, country-specific factors

We will investigate and describe initiation of first biologic treatment by asthma severity indicator over calendar time, also adjusted for age and gender. We will further explore whether this changes as quality of data improves and/or in response to key practice change initiatives (quality improvement, seminal papers). Asthma severity indicators will be defined using each of the following criteria: LTOCS use; pre-visit exacerbation(s); asthma control status; and lung function [FEV₁% predicted] (12).

6. Statistical Analysis

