issues) had any impact on data quality. We will also explore the effects of the confounder COVID and adjust for this, if necessary. Therefore, we will investigate how trends differ before and after a given intervention using a single group interrupted time series analysis (ITSA) using calendar year as the time variable. This will involve creating a spline of year with a knot placed at either one or several intervention periods and creating a variable to partition time periods to before and after the given intervention. Where the key period differs for each country (e.g. introduction of QI initiatives as part of the ISAR), we will explore changes either side of the key period (set to be time zero). A linear mixed effects model will be used to assess the percentage of variables that are complete (objective 2) by intervention period and covariates, modelling variation in country as a random effect. The odds of LTOC use (objective 3) pre- and post-intervention period will use a logistic mixed effects model, also using a random intercept for each country. For both methods, 95% confidence intervals will be calculated using bootstrapping techniques. For the time-to-event components of objective 3 (i.e. time from LTOCS to stopping/reducing LTOCS) and objective 4 (i.e. time to initiating biologic by asthma severity indicator), we will use time-to-event analyses (both non-parametric and flexible parametric methods).

Objective 1: Proportion of patients in ISAR with 100% completeness of key research variables from 1 May 2017 to latest date available

We will use data from the ISAR registry from May 2017 to the latest date available to calculate the proportion of patients in each calendar year with 100% completeness of key research variables from 1 May 2017 to latest data available. Reviews will be stratified into KPRs and RRs, and method of provision for each country (i.e. ISAR-built electronic data capture vs bespoke). Joinpoint analysis will be used to identify each calendar year period (i.e. the predictor variable) at which there is a change in the proportion of patients reaching 100% completeness and the size of this change (percentage change in rate per calendar year). A log-linear model will be used to analyse percentage change in rate over time, reporting on the linear trend in each segment, also stratifying by country to explore country-specific effects. We will also investigate specific inflection points/periods during the observation period using ITSA.

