Objective 2: Completeness of recording of all core variables in ISAR

Annual trends and changes in the proportion of core variables will be investigated in ISAR, also stratifying by country and provision of data method. The completeness of individual core variables will also be investigated to assess the variables that are least likely to be complete.

We will use a combination of joinpoint regression (to investigate trends) and ITSA (to investigate pre-specified inflection time points) with variation in country modelled as a random effect for this component of the analysis, also stratifying by data capture method. **Appendix 1** (Section 13.1) shows the complete list of core variables in ISAR.

Objective 3: Differences in the proportion of patients in ISAR who are prescribed LTOCS varies over time, and the characteristics of these patients

Trends in the proportion of patients with a LTOCS prescription in a given year (i.e. yes/no) and average dose of LTOCS will be described and plotted by calendar year using a combination of joinpoint regression and ITSA to analyse significant changes in trends, also stratifying by country-specific data capture method. For those on LTOCS, we will also investigate the probability of stopping/reducing LTOCS dose (<5mg) using time-to-event analysis (non-parametric [Kaplan-Meier] and flexible parametric methods). Patient characteristics for people with and without missing/incomplete data on LTOCS will also be compared.

Objective 4: Trends in the severity of asthma indicators in those initiating biologic treatment over time

The probability of initiating biologic treatments by asthma severity indicator and calendar year will be investigated using time-to-event analyses (non-parametric and flexible parametric models).

7. Regulatory and Ethical Compliance

This study was designed and shall be implemented and reported in accordance with the criteria of the “European Network Centres for Pharmacoepidemiology and Pharmacovigilance (ENCePP)” and follows the ENCePP Code of Conduct (EMA 2014). Once a final version of the protocol has been agreed and reviewed by the advisory group, this study will be registered with ENCePP (www.encepp.eu).

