POST-BD-FVC	Post-bronchodilator FVC							
ALLERGEN TESTING	Was an Environmental Allergen Test conducted?							
	-Positive to perennial allergen (Serum Allergen Test)?							
	+Specify perennial allergen (Serum Allergen Test) (Select all that apply)							
	-Positive to perennial allergen (SPT)?							
	+Specify perennial allergen (SPT) (Select all that apply)							
ASTHMA CONTROL	Asthma Control							
TREATMENT PLAN	What is the current Clinical Management Plan? (Select all that apply)							
LTOCS AND DAILY DOSE	Is the patient prescribed Maintenance Oral Steroids?							
	Daily dose of Maintenance Oral Steroids							
LTOCS NAME AND START DATE	Maintenance Oral Steroid name							

	Start Date of Maintenance Oral Steroids							
PRESCRIPTION ICS+LABA/ICS/LABA/LAMA/THEO/LTRA	Is the patient on a prescription for ICS+LABA combination therapy?							
	Is the patient on a prescription for ICS (only)?							
	Is the patient on a prescription for LABA (only)?							

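### Objective 3(ii) pools long-established and recently started LTOCS users, so a calendar trend in stopping or reducing could reflect a changing mix of users rather than changed practice

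*Protocol*

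**What the plan says.** - **Entry.** Protocol Section 4.2 drops a patient from Objective 3 if "they are not taking LTOCS at their baseline visit (defined by first visit with LTOCS=yes". Nothing restricts entry to recent starters.
- **Analysis set.** Section 6.3, Objective 3: "For those on LTOCS, we will also investigate the probability of stopping/reducing LTOCS dose (<5mg) using time-to-event analysis", with Kaplan-Meier and flexible parametric methods. All users form one group.
- **Time origin.** The general part of Section 6.3 describes the quantity as "time from LTOCS to stopping/reducing LTOCS", without saying whether the clock starts at the LTOCS start date or at the baseline visit.
- **Adjustment.** Section 5, Objective 3: "Covariates: Age, gender, country, country-specific factors". Neither prior LTOCS duration nor type of user appears.
- **Interpretation.** Section 5 evaluates stopping or dose reduction "of LTOCS to assess differences in clinical practice over calendar time".
- **Expected case-mix change.** The same section states: "The characteristics of patients in the ISAR registry who are prescribed LTOCS are likely to change with policy initiatives".
- **Visit type.** Section 3 undertakes to model whether a visit was a new-patient or a follow-up visit. Section 5 lists visit-specific factors as covariates for Objectives 1 and 2, but not for Objective 3.
- **Data held.** Table A1 in Appendix 1 includes "Start Date of Maintenance Oral Steroids" as a core variable, though not as a key research variable for either visit type. No definition for Objective 3 uses it.

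**The concern.** The entry rule admits two kinds of patient: those established on LTOCS before they came into view, some for years and having already passed earlier chances to taper, and those who started shortly before the baseline visit. Their chances of stopping or reducing may well differ. Calendar time is the exposure, so any change in the balance between the two groups enters the estimated trend directly, and none of the listed covariates removes it.

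The protocol intends to read that trend as a difference in clinical practice, while itself expecting the characteristics of LTOCS users to change. A trend produced by the mix could be reported as changed prescribing, or could hide a real change.

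**Working it through.** The protocol gives no stopping rate, event count or user mix for Objective 3(ii), so there is no figure of its own to reproduce. All inputs below are assumptions and serve only to show the range.

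**Step 1: effect of the mix with practice held constant.** Let pN and pL be the 12-month probabilities of stopping or reducing in newly started and long-established users, both fixed over calendar time. Let m be the share of newly started users. Then:

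- pooled probability P = m × pN + (1 − m) × pL
- odds ratio, late versus early = [P_late / (1 − P_late)] / [P_early / (1 − P_early)]

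Worked example with pN = 0.40, pL = 0.20 and m rising from 0.10 to 0.50:

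- early: 0.10 × 0.40 + 0.90 × 0.20 = 0.22
- late: 0.50 × 0.40 + 0.50 × 0.20 = 0.30
- odds ratio: (0.30/0.70) / (0.22/0.78) = 1.52

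| pN | pL | m early → late | P early → late | Odds ratio |
|---|---|---|---|---|
| 0.30 | 0.30 | 0.10 → 0.50 | 30% → 30% | 1.00 |
| 0.40 | 0.35 | 0.10 → 0.30 | 35.5% → 36.5% | 1.04 |
| 0.50 | 0.15 | 0.10 → 0.30 | 18.5% → 25.5% | 1.51 |
| 0.40 | 0.20 | 0.10 → 0.50 | 22% → 30% | 1.52 |
| 0.50 | 0.15 | 0.10 → 0.50 | 18.5% → 32.5% | 2.12 |
| 0.20 | 0.40 | 0.10 → 0.50 | 38% → 30% | 0.70 |

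For the 22% to 30% case, a comparison of two periods would give p < 0.05 with probability 82% at 500 patients per period and 98% at 1,000. Within each user group the calendar change is zero by construction, so the trend exists only in the pooled analysis.

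**Step 2: effect of the time origin, if the LTOCS start date were used.** Assume a constant stopping rate of 0.25 per year after entry. The true two-year probability is 1 − exp(−0.25 × 2) = 39.3%. In a simulation of 200,000 patients with exponentially distributed prior use:

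- clock at the baseline visit: about 39%, whatever the prior duration
- clock at LTOCS start, without delayed entry: 23.7%, 11.4% and 7.4% for mean prior use of 1, 3 and 5 years

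The shortfall arises because the years on LTOCS before entry are event-free by selection. It would then vary with calendar time whenever prior duration does.

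**The case against.** **Section 3 already promises a relevant term.** It says the modelling will account for new-patient versus follow-up visits and for when each country joined. A reader might infer from the Objective 3 covariate list that nothing in the plan separates the two kinds of user; Section 3 does not support that. Two limits remain: Section 5 does not carry the term into Objective 3, and it marks patients new to ISAR, who may have been on LTOCS for years.

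**The time origin may not be in conflict.** A reader might infer that Sections 4.2 and 6.3 contradict each other. The wording in Section 6.3 can equally be shorthand for the baseline visit that Section 4.2 defines, and no passage names the start date as origin. Step 2 therefore shows what is at stake in an ambiguity, not a bias in the stated analysis.

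**The mix need not shift as the registry ages.** A reader might infer that the share of newly started users must rise, because a first LTOCS record after an earlier visit without it needs follow-up. The documents do not show this. A follow-up visit can fall in a country's first year, a user at enrolment may have only just started, continuing enrolment keeps adding first-visit users, and fewer new LTOCS starts would push the other way.

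**Current users suit a descriptive objective.** The objective asks how the proportion stopped or reduced varies over time, and shorter prior use could itself reflect changed practice. This is fair, and is why the pooled estimate should be kept. It does not justify reading that estimate alone as a difference in practice.

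**This could be left to the SAP.** Much of the detail could. However, the protocol itself fixes the entry rule, the covariates and the interpretation, and these three do not fit together.

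**Conclusion.** The point holds as a risk of bias of unknown size and sign. It requires both that stop/reduce rates differ between long-established and recent users and that their mix changes over calendar time. The documents quantify neither. Under the assumed inputs the spurious odds ratio is 1.0 if the rates are equal, 1.04 if they are close, about 1.5 in moderate scenarios, 2.1 in the most extreme combination tried, and 0.7 if newly started users stop less often.

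A reader might infer that the bias must run towards more stopping, the result that would suit a registry whose mission is to reduce LTOCS exposure. That needs newly started users both to stop more readily and to form a growing share, and the documents support neither assumption.

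The change is worth making because it is cheap and uses data already held, and because the calendar trend is otherwise hard to interpret.

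**What to change.** 1. In Section 6.3, state that time zero for Objective 3(ii) is the baseline visit defined in Section 4.2. If the LTOCS start date is used instead, apply delayed entry at the baseline visit.
2. Define two classes from visit-level LTOCS status: on LTOCS at the first ISAR visit, and LTOCS first recorded as yes after a visit recorded as no. State where patients go whose earlier visits all have unknown status, since they fit neither class.
3. Stratify the Kaplan-Meier and flexible parametric analyses by this class and report the calendar-year effect within class.
4. Add LTOCS duration at baseline, from the collected start date, as a covariate where recorded. This is needed because the first class still mixes recent and long-standing users.
5. Report the pooled estimate alongside as descriptive.
6. Reconcile the Objective 3 covariate list in Section 5 with the visit-type term in Section 3.

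The cost is protocol wording and two derived variables (user class and prior duration). The downsides are smaller strata, which may limit country-level results, and start dates that may be incomplete, so the duration-adjusted result may rest on a subset. The user class itself needs only visit-level LTOCS status.

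### Objective 3(ii) times an absolute dose cut-off from an unrestricted starting dose but makes no provision for baseline dose, so drift in starting dose would mix with change in dose-reduction practice

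*Protocol*

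**What the plan says.** Section 2.2 gives Objective 3 two parts: (i) the proportion prescribed LTOCS over time and (ii) the proportion of LTOCS patients who stop or reduce over time.

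- **Event.** Section 5, Objective 3 plans to study time to "stopping/reducing the dose ($\leq 5\text{mg}$) of LTOCS to assess differences in clinical practice over calendar time". Section 6.3, Objective 3 describes the "probability of stopping/reducing LTOCS dose (<5mg) using time-to-event analysis". Both use a fixed daily dose, not a change from the patient's own baseline, and they differ on whether the cut-off value itself counts.
- **Time zero.** Section 4.2 excludes patients for Objective 3 if "they are not taking LTOCS at their baseline visit (defined by first visit with LTOCS=yes". No minimum dose is set.
- **Adjustment.** The Section 5 covariate line for Objective 3 reads "Covariates: Age, gender, country, country-specific factors". The text on trends in LTOCS use speaks of "adjusting for age and gender, and stratifying by country and country-specific factors". Section 6.3 names Kaplan-Meier and flexible parametric methods for stop/reduce, without covariates.
- **Expected change.** Section 5 states: "The characteristics of patients in the ISAR registry who are prescribed LTOCS are likely to change with policy initiatives".
- **Availability.** "Daily dose of Maintenance Oral Steroids" is in the LTOCS block of Table 1 and of Table A1 (Appendix 1), which is marked as a key variable at both key prior reviews and re-reviews. Section 6.3 also plans to plot average LTOCS dose by calendar year.

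**The concern.** Time to a fixed dose depends on how far above it the patient starts. Someone just above the cut-off may need one reduction; someone on several times that dose needs more. If patients entering in later years start on lower doses than those entering earlier, they reach the cut-off sooner even when clinicians reduce doses exactly as before. If they start on higher doses, a real improvement could be hidden.

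The stated use of this analysis is to assess clinical practice over calendar time. Without baseline dose, the reader cannot tell whether a calendar-year effect reflects how doses were reduced after entry or what doses patients were on when they entered.

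**Working it through.** The protocol gives no dose distribution, event rate or sample size for the stop/reduce analysis, so there is no figure of its own to reproduce. The check has a textual part and an illustrative part.

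**1. Text.** Baseline dose is absent from the Objective 3 covariate line, from the adjustment sentence in Section 5, and from the time-to-event text in Section 6.3. The plot of average dose by year is a separate description and does not enter the stop/reduce comparison.

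**2. Two-group illustration (all inputs assumed).** Dose-specific 12-month event probabilities are the same in every year, so practice does not change. The share starting on a lower dose rises from 40% to 70%. Pooled probability = share × p(lower) + (1 − share) × p(higher). The hazard ratio (HR), late versus early, is approximated by ln(1 − P late)/ln(1 − P early).

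| p(lower)/p(higher) | Early pooled | Late pooled | Apparent HR |
|---|---|---|---|
| 50%/40% | 0.4×0.50 + 0.6×0.40 = 0.44 | 0.7×0.50 + 0.3×0.40 = 0.47 | ln 0.53/ln 0.56 = 1.09 |
| 60%/30% | 0.4×0.60 + 0.6×0.30 = 0.42 | 0.7×0.60 + 0.3×0.30 = 0.51 | ln 0.49/ln 0.58 = 1.31 |
| 70%/20% | 0.4×0.70 + 0.6×0.20 = 0.40 | 0.7×0.70 + 0.3×0.20 = 0.55 | ln 0.45/ln 0.60 = 1.56 |

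If the drift runs the other way (70% to 40%), the middle row gives 1/1.31 = 0.76.

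**3. Stepwise illustration (all inputs assumed; a modelling device, not a suggested schedule).** Starting doses are 5/7.5/10/15/20 mg. The early mix is 15/15/30/20/20% (mean 11.88 mg) and the late mix 30/25/30/10/5% (mean 8.88 mg). Doses fall in 2.5 mg steps at 1.5 steps a year in both eras. Steps needed to reach 5 mg or less: k = (dose − 5)/2.5 = 0, 1, 2, 4, 6. Time to the cut-off is gamma with shape k and rate 1.5, so the one-year probabilities are 1, 0.777, 0.442, 0.066 and 0.004.

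- Early: 0.15×1 + 0.15×0.777 + 0.30×0.442 + 0.20×0.066 + 0.20×0.004 = 41.3%.
- Late: 0.30×1 + 0.25×0.777 + 0.30×0.442 + 0.10×0.066 + 0.05×0.004 = 63.4%.
- With the strict cut-off (below 5 mg), the same model gives 24.4% and 40.3%.

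Cox models were then fitted to one simulated data set per scenario (15,000 patients per era before dropping those starting at 5 mg; censoring at 2 years):

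| Part of the assumed shift that occurs | Unadjusted HR | HR stratified by starting dose |
|---|---|---|
| None | 0.98 | 1.00 |
| A quarter | 1.16 | 1.03 |
| Half | 1.29 | 0.99 |
| All | 1.70 | 1.02 |

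The apparent effect arises only with drift, and stratifying by starting dose removes it.

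**4. Patients already at the cut-off.** In this assumed mix, the 15% (early) and 30% (late) who start at 5 mg meet the inclusive wording at time zero; none do under the strict wording. The difference between the two wordings therefore also affects who is at risk at baseline.

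**The case against.** **The covariate line belongs to another outcome.** It stands under the proportion of patients on LTOCS at a visit, which is 3(i), and the adjustment sentence concerns trends in LTOCS use. Stop/reduce comes afterwards: "We will also evaluate proportion and time to stopping/reducing the dose". A reader might infer that the protocol fixes for 3(ii) a list that rules dose out. It does not: 3(ii) has no list of its own, and model terms can be left to a statistical analysis plan. What remains is that this is the only list under Objective 3, and that the protocol commits to an event definition and an interpretation whose validity depends on starting dose.

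**Drift is not documented.** A reader might infer that doses will shift, or that average dose is plotted because drift is expected. Section 5 speaks of patient characteristics in general, names neither dose nor direction, and Section 6.3 gives no reason for the plot. The plot could reveal drift among LTOCS users but would not correct the stop/reduce comparison.

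**Starting dose may itself be practice.** Section 5 allows that the registry may have changed clinicians' behaviour, so lower maintenance doses at entry may be part of the change under study. Adjusting would remove that part. This stands, and it rules out treating the adjusted effect as the only valid one.

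**Two further inferences lack support.** Nothing in the protocol shows that baseline dose is the strongest determinant of the event. Nor does it show that every before/after contrast around the quality initiatives is affected: the pre/post logistic model in Section 6.3 is for the odds of LTOCS use.

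**The event includes complete stopping.** True, so it is not purely a threshold. But the combined event is met on reaching the cut-off, so dependence on starting dose remains.

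**Conclusion.** The point holds conditionally. The absolute cut-off, the unrestricted starting dose and the absence of baseline dose from the stated adjustment are all in the text. If starting doses drift over calendar time, the calendar-year effect on stop/reduce combines two changes that the planned analysis cannot separate. Drift is plausible, because the protocol expects the LTOCS population to change, but it is not established.

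Size and direction are unknown from the documents. The two-group illustration gives a spurious HR of about 1.1 to 1.6 for drift towards lower doses; the stepwise model gives 1.16 to 1.70 depending on how much drift is assumed. Opposite drift would push the HR below 1, and no drift gives none of this bias. The analysis should be amended, but nothing here shows that its result will be wrong.

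**What to change.** For Objective 3(ii):

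1. Add daily dose at the baseline LTOCS visit as a covariate in the flexible parametric models, and show Kaplan-Meier curves by pre-set baseline-dose strata.
2. Report the dose-adjusted and unadjusted calendar-year effects side by side. Read the adjusted one as dose reduction given the starting dose, and the unadjusted one as also including changes in starting dose.
3. State how patients with no recorded baseline dose, and those who already meet the cut-off at baseline, are handled.
4. Reconcile the cut-off wordings in Section 5 and Section 6.3. No view is taken here on which is right.

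The cost is one more covariate, one more model term and a few sentences; daily dose is already collected. The downside is that patients on LTOCS with no recorded baseline dose drop out of the adjusted model or need imputation, so their number should be reported by calendar year.

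### Objective 4 treats asthma severity as present or absent, so a moderate fall in severity among patients starting biologics can be missed although graded data are recorded

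*Protocol*

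**What the plan says.** The Objective 4 heading in Section 6.3 reads "Trends in the severity of asthma indicators in those initiating biologic treatment over time", so the target is severity among initiators. The outcome in Section 5 is "Initiation of biologic treatment by asthma severity indicator". The domains are set there as follows: "Asthma severity indicators will be defined using each of the following criteria: LTOCS use; pre-visit exacerbation(s); asthma control status; and lung function", the last given as FEV1 % predicted. Each is used separately, with no grade or cut-point.

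The form of an indicator appears only in the Section 4.2 exclusion for Objective 4. Baseline is "defined by first visit with asthma severity indicator=yes", and patients with none of the indicators are left out. The analysis in Section 6.3 is: "The probability of initiating biologic treatments by asthma severity indicator and calendar year will be investigated using time-to-event analyses", by non-parametric and flexible parametric models.

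Table 1 lists as key research variables the number of steroid-treated exacerbations in 12 months, post-bronchodilator FEV1, asthma control and the daily dose of maintenance oral steroids. Section 6.3 plans average LTOCS dose by calendar year under Objective 3 but not under Objective 4.

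**The concern.** A present/absent indicator changes only when a patient crosses its cut-point. If biologics come to be started in patients with fewer exacerbations who still have at least one, or in LTOCS users on a lower dose, the indicator stays at yes and the change goes unrecorded. The Section 4.2 exclusion adds to this, because every patient analysed is at yes on at least one indicator.

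Earlier prescribing in less severe disease is the kind of practice change that Objective 4 sets out to describe. A flat result on yes/no indicators could be reported as stable severity at initiation when severity had fallen moderately, although the data that would show the fall are already in the registry.

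**Working it through.** The protocol gives no effect size, power or severity distribution for Objective 4, so there is no figure of its own to reproduce. The check asks how much a yes/no indicator loses against the recorded scale.

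**Assumptions (none from the protocol).** Yearly exacerbation counts are negative binomial with mean m and dispersion k. The indicator is at least one exacerbation. Two calendar periods have n = 400 initiators each, compared with a two-sided 5% test.

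**Formulas.**
- Share at yes: p = 1 − (1 + m/k)^(−k)
- Variance of the count: V = m + m²/k
- Power, yes/no: Φ(|p1 − p2| / √[(p1(1−p1) + p2(1−p2))/n] − 1.96)
- Power, count: Φ(|m1 − m2| / √[(V1 + V2)/n] − 1.96)

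**Moderate shift, mean 3.0 to 2.5, at k = 1.**
- p1 = 1 − 1/4 = 0.750 and p2 = 1 − 1/3.5 = 0.714. The difference is 0.036 with standard error 0.0313, so z = 1.14 and power = Φ(−0.82) = 21%.
- V1 = 3 + 9 = 12 and V2 = 2.5 + 6.25 = 8.75. The difference is 0.5 with standard error √(20.75/400) = 0.228, so z = 2.20 and power = Φ(0.24) = 59%.

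| k | Share with at least one | Power, yes/no | Power, count |
|---|---|---|---|
| 1 | 75.0% to 71.4% | 21% | 59% |
| 2 | 84.0% to 80.2% | 28% | 79% |
| 5 | 90.5% to 86.8% | 37% | 93% |

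**A somewhat larger shift, mean 4 to 3, with 300 per period.** Power is 31% against 86% at k = 1, and 42% against 98% at k = 2.

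**A large shift, mean 4 to 2, with 300 per period.** The share at yes falls from 80.0% to 66.7% at k = 1 and from 88.9% to 75.0% at k = 2. Power for yes/no is 96% and 99%. Halving the mean is seen either way.

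**Larger samples.** Section 6.1 counts 3,036 switch or new-biologic visits. Half of that, 1,518 per period, is only a rough scale, because it mixes starts with switches and may omit starts at first visits. At that size, 3.0 to 2.5 with k = 1 gives 60% against 99%. Strata by country or single year would be smaller.

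**FEV1 % predicted.** Assume a normal distribution with SD 20 and a cut at 80%, borrowed from the entry criteria. A rise in mean from 70 to 75 moves the share below 80% from 69.1% to 59.9%. With 300 per period, power is 66% for yes/no against 86% for the mean, so the loss is smaller than for counts.

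**LTOCS dose.** No distribution is needed. A fall in dose among patients still on LTOCS leaves the LTOCS-use indicator unchanged.

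**The case against.** The strongest objection is that yes/no coding of the analysis variable is inferred. The wording comes from an exclusion criterion that fixes the baseline visit. FEV1 % predicted and control status in Section 5 could be read as graded, and functional form is often left to an SAP, which is not shown. This stands in part: missing cut-points are no fault. But presence/absence is the only form the protocol states, it conditions the cohort on at least one yes, and the Objective 4 analysis mentions no graded measure.

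A second objection also stands. The calculation compares initiators in two periods, whereas the planned model is time to initiation and includes patients who have not started. Earlier prescribing could appear there as rising initiation among patients who lack a given indicator. The power figures therefore illustrate the loss of information; they are not the power of the planned model.

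A reader might go further and infer that the indicators repeat the entry criteria, sit near their ceiling by design, and hide most real change. The documents do not support that. Three of the four domains do overlap with the Step 4 criteria, such as "frequent exacerbations: two or more bursts of systemic corticosteroids (>3 days each) in the previous year". But any one Step 4 criterion suffices, Step 5 patients enter with none of these criteria attached, and LTOCS use is not a listed entry criterion. Entry therefore fixes no single indicator at yes. Each indicator is examined separately, so its share can move, and large shifts are detected.

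**Conclusion.** The point holds as an improvement to the plan. As written, Objective 4 is insensitive to change among patients who remain at yes, so a moderate fall in severity at initiation can be missed and a null result misread as stable severity. In the illustrated exacerbation example the count has about 2.5 to 2.8 times the power of the indicator (59/21 = 2.8; 93/37 = 2.5). The loss is smaller for FEV1 and complete for dose change within LTOCS users. The sizes rest on assumed distributions, a cut at one exacerbation and a simple two-period comparison. The direction held in every scenario of moderate change that was tried. It does not follow that Objective 4 would fail to see a large change.

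**What to change.** In Section 5 (Objective 4) and Section 6.3 (Objective 4):

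- Keep the yes/no indicators for eligibility and display, and say explicitly that this is their role.
- Add, among first-biologic initiators, the distribution by calendar year of exacerbation count, FEV1 % predicted, LTOCS daily dose and asthma control category, adjusted for age and gender, the covariates Objective 4 already uses.
- Enter these variables on their recorded scale, with control as ordered categories and splines for continuous measures, in the flexible parametric model with a calendar-time interaction.
- Report the number with each value missing by year, since completeness is itself expected to change over the study.

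No new data collection is needed. The cost is protocol or SAP wording, modest extra analysis, and a presentation slightly harder to read than yes/no groups.
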